4.2.2 Concomitant Medications

4.2.2.1 Corticosteroids: Patients receiving corticosteroids who have not been on a stable or decreasing dose of corticosteroid for at least 7 days prior to enrollment are not eligible. If used to modify immune adverse events related to prior therapy, \geq 14 days must have elapsed since last dose of corticosteroid (See Section [4.1.6.1.d](#)).

4.2.2.2 Investigational Drugs: Patients who are currently receiving another investigational drug are not eligible.

4.2.2.3 Anti-cancer Agents: Patients who are currently receiving other anti-cancer agents are not eligible.

4.2.2.4 Anti-GVHD agents post-transplant:

Patients who are receiving cyclosporine, tacrolimus or other agents to prevent graft-versus-host disease post bone marrow transplant are not eligible for this trial.

4.2.3 Infection: Patients who have an uncontrolled infection are not eligible.

4.2.4 Diabetes: Patients who have insulin dependent diabetes are not eligible.

4.2.5 Patients who have received a prior solid organ transplantation are not eligible.

4.2.6 Patients with SubEpendymal Giant cell Astrocytomas (SEGAs) are not eligible because everolimus is approved by the FDA for this patient population.

4.2.7 Patients who in the opinion of the investigator may not be able to comply with the safety monitoring requirements of the study are not eligible.

5.0 TREATMENT PROGRAM

5.1 Overview of Treatment Plan

Day 1-28	Day 28
LY3023414 orally, twice daily	Evaluation

LY3023414 will be administered orally twice daily. For patients enrolled during the dose-confirmation part of the study, the Cycle 1 Day 1 PM dose of LY3023414 will be omitted for PK sampling.

Therapy will be discontinued if there is evidence of progressive disease or drug related dose-limiting toxicity that requires removal from therapy ([Section 6.0](#)). Therapy may otherwise continue for a maximum of 6 cycles provided the patient meets the criteria for starting subsequent cycles ([Section 5.2](#)) and does not meet any of the criteria for removal from protocol therapy criteria ([Section 10.0](#)).

A cycle of therapy is considered to be 28 days. A cycle may be repeated for a maximum of 6 cycles.

Drug doses should be adjusted based on the BSA calculated from height and weight measured within 7 days prior to the beginning of each cycle, and according to the dosing nomogram (see [Appendix IV](#)).

LY3023414 should be taken without regards to food with a glass of water at approximately the same time each day. Patients should swallow the tablets as a whole and should not chew or crush them.

If a patient misses a dose of LY3023414, the dose should be taken as soon as possible as long as it is more than 6 hours before the next scheduled dose. If it is less than 6 hours before the next dose, then the dose should be skipped. If vomiting occurs after taking LY3023414, the patient should skip the dose and take the next dose as scheduled.

5.1.1 Determination of Recommended Phase 2 Dose (RP2D)/Tolerable Dose

Dose Level	Dose (mg/m ²)
-1	55 mg/m ² /dose BID
1*	80 mg/m ² /dose BID
2	115 mg/m ² /dose BID

Update (Amendment 5A): There were no cycle 1 dose limiting toxicities in the patients enrolled to either dose level 1 or dose level 2 during dose determination. Therefore, the RP2D on this study has been determined to be dose level 2 (115mg/m²/dose BID), and all remaining subjects will enroll at this dose.

The DLT evaluation period for the purpose of dose escalation will be cycle 1 of therapy. Patients enrolled during the determination of the recommended phase 2

[figure not shown]
dose who are not evaluable for toxicity during cycle 1 at a given dose level will be replaced.

The starting dose will be 80 mg/m²/dose BID (Dose Level 1), which is approximately 30% below the adult MTD. Accrual will be temporarily suspended after enrollment to the first 6 toxicity-evaluable subjects to assess for toxicity as outlined in [Section 11.2](#).

If there are fewer than 2 DLTs in the first 6 toxicity-evaluable subjects enrolled at the starting dose, the dose will be escalated to Dose Level 2. If ≥ 2 of the first 6 toxicity-evaluable subjects enrolled at Dose Level 2 have DLTs, all subsequent subjects will be enrolled at the original starting dose. Otherwise, remaining subjects will continue to enroll at Dose Level 2.

If there are 2 or more DLTs during cycle 1 among the first 6 toxicity-evaluable subjects enrolled at Dose Level 1, the next cohort will enroll at Dose Level -1. If ≥ 2 of the first 6 toxicity-evaluable subjects enrolled at the reduced dose have DLTs, the study will be closed for toxicity. Otherwise, remaining subjects will continue to enroll at Dose Level -1.

Dose escalation schema:

5.1.2 Intra-Patient Escalation

Intra-patient dose escalation is not allowed.

5.1.3 Therapy Delivery Map

See [Appendix VI](#) for APEC1621D Therapy Delivery Map.

5.2 Criteria for Starting Subsequent Cycles

A cycle may be repeated every 28 days if the patient has at least stable disease and has again met laboratory parameters as defined in the eligibility section, [Section 4.0](#) with the exception of hyperglycemia, hypercholesterolemia, and hypertriglyceridemia, for which the patient may proceed to the next cycle as long as there is not an ongoing dose limiting toxicity as defined in [Section 5.4.1](#).

5.3 Grading of Adverse Events

Adverse events (toxicities) will be graded according to the current version of the NCI Common Terminology Criteria for Adverse Events (CTCAE). All appropriate treatment areas should have access to a copy of the current version of the CTCAE v5.0. A copy of the CTCAE v5.0 can be downloaded from the CTEP website (<http://ctep.cancer.gov>). Any suspected or confirmed dose-limiting toxicity should be reported immediately (within 24 hours) to the Study Chair.

5.4 Definition of Dose-Limiting Toxicity (DLT)

DLT will be defined as any of the following events that are possibly, probably or definitely attributable to protocol therapy. Dose limiting hematological and non-hematological toxicities are defined differently.

5.4.1 Non-Hematological Dose-Limiting Toxicity

5.4.1.1 Any Grade 4 or greater non-hematological toxicity attributable to the investigational drug with the specific exclusion of:

- Grade 4 fever < 5 days duration.
- Hyperglycemia >500 mg/dL (>27.8 mmol/L) that returns to fasting glucose value \leq 250 mg/dL (13.9 mmol/L) within 24 hours of initiation of appropriate supportive care as per Section 7.3.4. The severity (grade) of hyperglycemia is based upon fasting levels. If glucose >500 mg/dL (>27.8 mmol/L) is detected when routine (non-fasting) laboratory studies are performed, the test should be repeated within 24 hours in the fasting state to permit accurate grading.

Grade 4 hypercholesterolemia that returns to \leq Grade 2 within 35 days of initiation of appropriate supportive care as per [Section 7.3.6](#). The severity (grade) of hypercholesterolemia is based upon fasting levels. If Grade 4 hypercholesterolemia is detected when routine (non-fasting) laboratory studies are performed, the test should be repeated within 3 days in the fasting state to permit accurate grading.

5.4.1.2 Any Grade 3 non-hematological toxicity attributable to the investigational drug with the specific exclusion of:

- Nausea, vomiting, diarrhea, constipation, or anorexia of \leq 3 days duration
- Fatigue that resolves to \leq Grade 2 within 7 days
- Oral or pharyngeal mucositis or stomatitis \leq 7 days duration
- Liver enzyme elevation, including ALT/AST/GGT that returns to levels that meet initial eligibility criteria or baseline within 7 days. See [Appendix X](#) for values that represent thresholds between CTCAE grades.

Note: For the purposes of this study the ULN for ALT is defined as 45 U/L regardless of baseline.

- Fever < 5 days duration.
- Infection < 5 days duration.

- Hypophosphatemia, hypokalemia, hypocalcemia or hypomagnesemia responsive to supplementation.
- Hyperglycemia that returns to fasting glucose value ≤ 250 mg/dL (13.9 mmol/L) (with or without the use of insulin or oral diabetic agents) within 7 days of initiation of appropriate supportive care as per [Section 7.3.4](#). The severity (grade) of hyperglycemia is based upon fasting levels. If glucose in the range $>250 - 500$ mg/dL; ($>13.9 - 27.8$ mmol/L) is detected when routine (non-fasting) laboratory studies are performed, the test should be repeated within 3 days in the fasting state to permit accurate grading.
- Hypertriglyceridemia that returns to Grade ≤ 2 within 14 days of initiation of appropriate supportive care as per [Section 7.3.5](#). The severity (grade) of hypertriglyceridemia is based upon fasting levels. If Grade 3 triglycerides are detected when routine (non-fasting) laboratory studies are performed, the test should be repeated within 3 days in the fasting state to permit accurate grading.
- Hypercholesterolemia that returns to \leq Grade 2 within 35 days of initiation of appropriate supportive care as per [Section 7.3.6](#). The severity (grade) of hypercholesterolemia is based upon fasting levels. If Grade 3 hypercholesterolemia is detected when routine (non-fasting) laboratory studies are performed, the test should be repeated within 3 days in the fasting state to permit accurate grading.
- Papulopustular, acneiform, or maculo-papular rash that resolves to $<$ Grade 2 or baseline within 14 days of appropriate supportive care as per [Section 7.3.2](#). However, any investigational drug-related grade 3 rash that is considered intolerable by the patient or limits ADLs will be considered a DLT regardless of duration.

5.4.1.3 Any Grade 2 non-hematological toxicity that persists for ≥ 7 days and is considered sufficiently medically significant or sufficiently intolerable by patients that it requires treatment interruption.

- Note: Allergic reactions that necessitate discontinuation of study drug will not be considered a dose-limiting toxicity.

5.4.2 Hematological dose limiting toxicity

5.4.2.1 Hematological dose limiting toxicity is defined as:

- a) In patients evaluable for hematological toxicity (see [Section 4.1.7.1](#)),
 - Grade 4 thrombocytopenia or neutropenia, not due to malignant infiltration.
 - Grade 3 thrombocytopenia that persists for ≥ 7 days
 - Grade 3 thrombocytopenia requiring a platelet transfusion on two separate days within a 7-day period
 - Grade 3 thrombocytopenia with clinically significant bleeding
 - Neutropenia or thrombocytopenia that causes a delay of > 14 days between treatment cycles.

5.4.2.2 Note: Grade 3 or 4 febrile neutropenia will not be considered a dose-limiting toxicity.

6.0 DOSE MODIFICATIONS FOR ADVERSE EVENTS

The Study Chair must be notified of any dosage modification or use of myeloid growth factor.

6.1 Dose Modifications for Hematological Toxicity

- 6.1.1 If a patient experiences hematological dose-limiting toxicity as defined in [Section 5.4.2](#), the treatment will be held. Counts should be checked every 3-4 days for thrombocytopenia and every other day for neutropenia during this time. If the toxicity resolves to meet eligibility parameters within 14 days of drug discontinuation, the patient may resume treatment at a reduced dose as outlined in the dose reduction table ([Appendix IV](#)). Doses reduced for toxicity will not be re-escalated, even if there is minimal or no toxicity with the reduced dose.
- 6.1.2 If toxicity does not resolve to meet eligibility parameters within 14 days of drug discontinuation, the patient must be removed from protocol therapy.
- 6.1.3 If hematological dose-limiting toxicity recurs in a patient who has resumed treatment at the reduced dose, the patient must be removed from protocol therapy.

6.2 Dose Modifications for Non-Hematological Toxicity

- 6.2.1 If a patient experiences non-hematological dose-limiting toxicity as defined in [Section 5.4.1](#), the treatment will be held. When the toxicity resolves such that there is no ongoing DLT of hyperglycemia, hypercholesterolemia, and hypertriglyceridemia as defined in [Section 5.4.1](#) and other laboratory values meet eligibility parameters or baseline within 14 days of drug discontinuation, the patient may resume treatment at a reduced dose as outlined in the dose reduction table ([Appendix IV](#)). Doses reduced for toxicity will not be re-escalated, even if there is minimal or no toxicity with the reduced dose.
- 6.2.2 If toxicity does not resolve such that there is no ongoing DLT of hyperglycemia, hypercholesterolemia, and hypertriglyceridemia as defined in [Section 5.4.1](#) and other laboratory values meet eligibility parameters or baseline within 14 days of drug discontinuation, the patient must be removed from protocol therapy.
- 6.2.3 If dose-limiting toxicity recurs in a patient who has resumed treatment at the reduced dose, the patient must be removed from protocol therapy.
- 6.2.4 If a patient experiences a Grade 2 or greater allergic reaction to LY3023414, the patient will be removed from protocol therapy.

7.0 SUPPORTIVE CARE AND OTHER CONCOMITANT THERAPY

7.1 Concurrent Anticancer Therapy

Concurrent cancer therapy, including chemotherapy, radiation therapy, immunotherapy, or biologic therapy may NOT be administered to patients receiving study drug. If these treatments are administered the patient will be removed from protocol therapy.

7.2 Investigational Agents

No other investigational agents may be given while the patient is on study.

7.3 Supportive Care

Appropriate antibiotics, blood products, antiemetics, fluids, electrolytes and general supportive care are to be used as necessary. See [Section 7.5](#) for drugs that should not be used concomitantly due to potential interactions with LY3023414. See below for recommendations on management of specific toxicities associated with LY3023414.

7.3.1 Nausea and vomiting:

Nausea and vomiting has been observed frequently in adult patients treated with LY3023414. It is recommended to provide all patients a 5-HT₃-Receptor blocker (eg, ondansetron or granisetron) at the start of treatment to be used as needed or prophylactically. In the event of breakthrough nausea/vomiting, additional antiemetics may be added as needed.

7.3.2 Rash:

Rashes which can be pruritic have been observed infrequently in adult patients treated with LY3023414. For all patients, prophylactic measures should be considered including the use of sunscreen prior to any sun-exposure and application of thick emollient cream to dry areas of the body at least twice daily. For grade 1 rash, mild-moderate potency topical steroids and oral antihistamines (if pruritic) should be considered. For grade 2 rash, moderate potency topical steroids and oral antihistamines (if pruritic) are recommended. For grade 3 rash, moderate potency topical steroids should be applied at least twice daily and oral antihistamines should be used if the rash is pruritic. Patients with a grade 3 or worse rash should have a physical exam at least weekly until improvement to grade ≤ 2 . As per [section 5.4.1.1](#), any grade 3 rash that is intolerable, limiting ADLs, or that persists for > 14 days after initiation of topical steroid therapy will be considered a dose limiting toxicity. LY3023414 will be held and moderate potency topical steroids will be applied at least twice daily and a course of systemic steroid should be strongly considered with oral antihistamines given as needed for pruritis.

7.3.3 Mucositis:

Mucositis has been observed in adult patients treated with LY3023414. For grade 1 mucositis, it is recommended to use conservative measures such as non-alcoholic mouth wash or salt water (0.9%) mouth wash several times a day until resolution. For grade ≥ 2 mucositis, topical analgesic mouth treatments (i.e., local anesthetics such as benzocaine, butyl aminobenzoate, tetracaine hydrochloride, menthol, or phenol) may be used with or without topical corticosteroids, such as triamcinolone oral paste 0.1% (e.g. Kenalog in Orabase®). Agents containing hydrogen peroxide, iodine, and thyme derivatives may worsen mouth ulcers and should not be used.

Systemic antifungal agents should be avoided unless a fungal infection is diagnosed.

In particular, systemic imidazole antifungal agents (ketoconazole, fluconazole, itraconazole, etc.) should be avoided due to their strong inhibition of CYP3A4 metabolism, therefore leading to higher LY3023414 exposure. Topical antifungal agents are preferred if an infection is diagnosed.

7.3.4 **Hyperglycemia:**

Hyperglycemia has been observed in adults treated with LY3023414. **Initiation of treatment for hyperglycemia should occur under the guidance of a pediatric endocrinologist at the local institution.** Metformin or other oral anti-hyperglycemia agent may be used per local endocrinologist's recommendations. Insulin therapy should be directed by specialists in pediatric diabetes, with the goal of normal fasting blood sugars < 126 mg/dL and HgbA1C < 8%.

For fasting glucose value \leq 160 mg/dL (8.9 mmol/L), conservative measures are recommended (dietary modification). For fasting glucose value $>160 - \leq 250$ mg/dL ($>8.9 - \leq 13.9$ mmol/L), consultation with an endocrinologist and consideration of initiation of an oral anti-diabetic agent is recommended. Insulin therapy should be considered if treatment with an oral anti-diabetic is insufficient. For glucose in the range $>250 - 500$ mg/dL; ($>13.9 - 27.8$ mmol/L) or glucose >500 mg/dL (>27.8 mmol/L) persisting less than 24 hours, insulin or an oral anti-diabetic agent should be started in consultation with an endocrinologist. Patients with glucose in the range $>250 - 500$ mg/dL; ($>13.9 - 27.8$ mmol/L) or worse hyperglycemia should have fasting glucose checked at least twice weekly until resolution to less than or equal to a fasting glucose value ≤ 250 mg/dL (13.9 mmol/L). Glucose in the range $>250 - 500$ mg/dL; ($>13.9 - 27.8$ mmol/L) persisting for more than 7 days after starting an oral antidiabetic agent and glucose >500 mg/dL (>27.8 mmol/L) persisting for more than 24 hours after starting an oral antidiabetic agent are a dose limiting toxicities. LY3023414 will be held and the patient will be treated with insulin or an oral anti-diabetic agent in consultation with an endocrinologist.

7.3.5 **Hypertriglyceridemia:**

Hypertriglyceridemia has been observed in patients treated with mTOR inhibitors. **Initiation of treatment for hypertriglyceridemia should occur under the guidance of pediatric specialists with expertise in lipid disorders at the local institution.**

For grade 2 hypertriglyceridemia, consultation with a pediatric specialist with expertise in lipid disorders and consideration of initiation of an HMG-CoA reductase inhibitor is recommended. For grade 3 hypertriglyceridemia, an HMG-CoA reductase inhibitor should be started in consultation with a pediatric specialist with expertise in lipid disorders. Patients with grade 3 or worse hypertriglyceridemia should have fasting triglycerides checked at least weekly until resolution to \leq grade 2. Grade 3 hypertriglyceridemia persisting for more than 14 days after starting an HMG-CoA reductase inhibitor and any grade 4 hypertriglyceridemia are a dose limiting toxicities. LY3023414 will be held and the patient will be treated with an HMG-CoA reductase inhibitor in consultation with a pediatric specialist with expertise in lipid disorders.

7.3.6 **Hypercholesterolemia:**

Hypercholesterolemia has been observed in patients treated with mTOR inhibitors. **Initiation of treatment for hypercholesterolemia should occur under the**

guidance of pediatric specialists with expertise in lipid disorders at the local institution.

For grade 2 hypercholesterolemia, consultation with a pediatric specialist with expertise in lipid disorders and consideration of initiation of an HMG-CoA reductase inhibitor is recommended. For grade 3 or 4 hypercholesterolemia, an HMG-CoA reductase inhibitor should be started in consultation with a pediatric specialist with expertise in lipid disorders. Patients with grade 3 or worse hypercholesterolemia should have fasting cholesterol checked at least every other week until resolution to \leq grade 2. Grade 3 or 4 hypercholesterolemia persisting for more than 35 days after starting an HMG-CoA reductase inhibitor is a dose limiting toxicity. LY3023414 will be held and the patient will be treated with an HMG-CoA reductase inhibitor in consultation with a pediatric specialist with expertise in lipid disorders.

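### Section 7.3.4 restates the 24-hour hyperglycemia DLT and hold trigger differently from the governing definition in Section 5.4.1

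*Combined protocol and SAP*

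**What the plan says.** Section 5.4.1.1 opens with a general rule, "Any Grade 4 or greater non-hematological toxicity attributable to the investigational drug with the specific exclusion of", and then lists exclusions. One of them is "Hyperglycemia >500 mg/dL (>27.8 mmol/L) that returns to fasting glucose value" of 250 mg/dL or lower "within 24 hours of initiation of appropriate supportive care as per Section 7.3.4". Section 5.4.1.2 has the parallel exclusion for the range above 250 to 500 mg/dL: recovery to fasting 250 or lower within 7 days, "with or without the use of insulin or oral diabetic agents". Severity is graded on fasting values in both.

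Section 6.2.1 attaches the hold to this definition: "If a patient experiences non-hematological dose-limiting toxicity as defined in" Section 5.4.1, treatment is held and may resume only at a reduced dose, with no later re-escalation. Section 5.2 uses the same definition for starting the next cycle.

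Section 7.3.4 gives its own DLT wording. It names two events: glucose above 250 to 500 mg/dL lasting more than 7 days after an oral agent is started, and "glucose >500 mg/dL (>27.8 mmol/L) persisting for more than 24 hours after starting an oral antidiabetic agent are a dose limiting toxicities". The instruction to hold drug follows. For the shorter case it says that for "glucose >500 mg/dL (>27.8 mmol/L) persisting less than 24 hours, insulin or an oral anti-diabetic agent should be started in consultation with an endocrinologist". On monitoring, patients above 250 mg/dL "or worse hyperglycemia should have fasting glucose checked at least twice weekly until resolution" to a fasting value of 250 or lower.

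**The concern.** The two sections use different recovery levels for the same 24-hour window. Section 5.4.1.1 requires a fall to 250 mg/dL or lower. Section 7.3.4, read literally, is satisfied once glucose is no longer above 500. A patient who lands between the two is a DLT in one section and only a treated patient in the other.

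The starting point differs too. Section 5.4.1.1 counts from the start of supportive care. Both clocks in 7.3.4 count from an oral agent, although the same paragraph allows insulin as first treatment.

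At stake are the hold, the permanent dose reduction and the DLT report to the Study Chair within 24 hours under Section 5.3. A site managing this event is pointed to 7.3.4 by the DLT definition itself and finds directive DLT and hold wording there.

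**Working it through.** The plan states no figure to reproduce. The check applies the literal wording of the two sections to each possible 24-hour outcome.

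**Case.** Fasting glucose above 500 mg/dL, attributable to the drug, treated at hour 0.

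| Fasting glucose at 24 hours | Under 5.4.1.1 | 24-hour trigger in 7.3.4 | Result |
|---|---|---|---|
| 250 or lower | excluded, not a DLT | not met | agree |
| above 250 to 500 (e.g. 520 falling to 400) | exclusion not met, so DLT and hold | not met | conflict |
| still above 500 | DLT and hold | met once past 24 hours, if an oral agent was started | agree, unless insulin alone was given |

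The 7-day exclusion in 5.4.1.2 does not rescue the middle row, because it belongs to the Grade 3 list and 5.4.1.1 places values above 500 in the Grade 4 list.

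**Comparison with the lipid sections.** Section 7.3.6 puts Grade 3 and Grade 4 hypercholesterolemia under one 35-day clock, so a fall from Grade 4 to Grade 3 still counts, as in 5.4.1. Section 7.3.5 also matches 5.4.1. Only 7.3.4 gives the two ranges separate clocks and so loses the step-down case.

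**Monitoring.** The fasting repeat within 24 hours in 5.4.1.1 serves to grade a non-fasting value. It does not ask for a value 24 hours after treatment starts. The twice-weekly minimum in 7.3.4 does not guarantee one.

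**Illustrative delay.** Assume an oral agent at hour 0, a fall to 400 mg/dL at 24 hours, no later recovery, and a site that follows 7.3.4 alone. The next trigger comes after day 7.
- Extra time on drug: 7 − 1 = 6 days.
- Doses at twice daily: 6 × 2 = 12.
- At 115 mg/m² per dose (Section 5.1.1): 12 × 115 = 1,380 mg/m².
- Across the Dose Level 2 bands of Appendix IV (100 to 400 mg/day): 6 × 100 = 600 mg to 6 × 400 = 2,400 mg.

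**Dose cut that depends on the call** (Appendix IV, Dose Level 2, mg/day):
- 100 to 50: 50/100 = 50%
- 150 to 100: 50/150 = 33%
- 200 to 150: 50/200 = 25%
- 300 to 200: 100/300 = 33%
- 400 to 300: 100/400 = 25%

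**Patients concerned.** Section 11.1 sets a maximum of 24. Dose finding used 12 toxicity-evaluable patients (6 at each of two levels, taken as complete because the RP2D is declared), so at most 24 − 12 = 12 enrol after it. Dose-finding patients still on drug, for up to 6 cycles, fall under the same rules, so 12 does not cap the number affected.

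**The case against.** **A consistent reading is available.** The monitoring sentence in 7.3.4 covers everyone above 250 mg/dL and ends at a fasting value of 250 or lower. On that footing, persistence could mean that an episode has not yet resolved, which would restore the 5.4.1.1 rule. This shows that some sites may act correctly. It strains the text, however: the DLT sentence gives the range above 250 to 500 its own 7-day clock and attaches the 24-hour clock to values above 500. The treatment step for values above 500 lasting under 24 hours is also the same as for the lower range, with no hold.

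**The matter is governed elsewhere.** Sections 5.4, 6.2.1 and 5.2 control the DLT call, the hold and the next cycle, while 7.3 describes itself as recommendations. Section 5.3 asks for suspected as well as confirmed DLTs to be reported within 24 hours, so the Study Chair may be involved early. Section 14.4.2 adds the Study Chair's own DLT evaluation, and a pediatric endocrinologist guides treatment. All of this stands, and it is why the impact is low. Later review can correct a classification but cannot recall doses already taken.

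**Exposure looks small.** Entrants must have normal glucose (Section 4.1.7.4). The risk list in Section 9.1.9 puts hyperglycemia in the column for 20% or less, based on 165 patients, without isolating values above 500 mg/dL. This stands.

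**Stronger readings that the documents do not support.** A reader might infer that the RP2D is in doubt. Section 5.1.1 records no cycle 1 DLTs at either dose level, dose escalation used the 5.4 definition, and nothing suggests that a glucose event was misclassified. A reader might also take 6 days as the worst case. It is not: with insulin alone the literal 7.3.4 clocks never start, and a patient who reaches 250 or lower by day 7 is never held under 7.3.4.

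**Conclusion.** Section 7.3.4 is wrong as written, with low practical impact. An attributable fasting glucose above 500 mg/dL that has fallen only to above 250 to 500 mg/dL at 24 hours requires a hold and dose reduction under 5.4.1.1 and 6.2.1, yet does not meet the 24-hour trigger in 7.3.4. Its two clocks also ignore insulin as first treatment.

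The effect is confined to holds, dose reductions and DLT reporting in patients still on treatment or yet to start. The primary endpoint and the RP2D are unaffected. The number of events above 500 mg/dL is not in the documents, so no expected count can be given.

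The conclusion assumes that the event is attributable and that a fasting value above 500 is Grade 4. Section 5.4.1.1 implies the grade by placing the exclusion in its Grade 4 list; Appendix XI has no glucose row to confirm it. If a site graded the event 3, the 7-day rule would apply and this 24-hour conflict would not arise.

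**What to change.** In Section 7.3.4, replace the DLT sentence with one that defers to Section 5.4.1 and repeats its criteria. Hyperglycemia is dose limiting, as defined in 5.4.1, in either of these cases:
- an attributable fasting glucose above 500 mg/dL does not come back to fasting 250 mg/dL or lower within 24 hours;
- an attributable fasting glucose above 250 to 500 mg/dL does not do so within 7 days.

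Both clocks should run from the start of appropriate supportive care, stated to include insulin or an oral agent. The fasting and attribution conditions need to be kept, or the new sentence would introduce a fresh mismatch.

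Add one sentence requiring a fasting glucose 24 hours after treatment starts for any fasting value above 500 mg/dL. With these changes, all three 24-hour outcomes are classified alike in both sections.

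The cost is one sentence replaced, one added, and one fasting glucose test per event above 500 mg/dL.
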